## STUDY PROTOCOL

### 1. BACKGROUND AND RATIONALE

#### 1.1. General Introduction

Arthroscopic technique is being utilized more to treat a wide variety of pathologic conditions of the shoulder. Adequate visual clarity is imperative to safely and effectively perform arthroscopic shoulder surgery. Addition of epinephrine to the arthroscopic irrigation can help to improve visual clarity [1-4].

#### 1.2. Rationale and justification for the Study

##### a. Rationale for the Study Purpose

Addition of epinephrine to arthroscopic irrigation raises the cost of the procedure and has the potential for rare, but serious, cardiovascular adverse events [5-9]. We have also used a subacromial injection of bupivacaine epinephrine prior to the initiation of the surgical procedure. This helps us limit the use of epinephrine to the first 6 liters of irrigation fluid. In this way, we limit the cost of the surgery as well as the total dose of epinephrine to decrease the likelihood of epinephrine-related adverse events, without sacrificing visual clarity. Additionally, when visualization is limited, surgeons may increase the pump pressure of arthroscopic fluid within the shoulder. This increases fluid extravasation into the surrounding soft tissues, and can cause difficulties with surgical exposure. We propose a double-blinded, randomized controlled trial to compare the use of subacromial injection of bupivacaine with and without epinephrine to determine the effectiveness in terms of visual clarity.

##### b. Rationale for Doses Selected

The dose of bupivacaine with epinephrine to be injected into the subacromial space prior to surgery will be the standard dose we have administered as part of our routine surgical protocol. The dose of epinephrine injected into the subacromial space will be 0.3 mg of epinephrine in 30mL of 0.5% bupivacaine for a dilution of 1:100. A total volume of 20 mL of the mixed solution will be injected into the subacromial space prior to the start of the surgery. The dose of epinephrine to be used in the arthroscopic irrigation fluid is 5 mL of epinephrine in 5 liters of sterile saline for a dilution of 1:1000. These doses of epinephrine in the subacromial injection as well as the arthroscopic irrigation fluid have been used for several years by the study investigators without any epinephrine-related cardiovascular adverse events. By limiting the use of epinephrine to the pre-operative injection and the first 10 liters of arthroscopic irrigation only as opposed to using epinephrine in the irrigation fluid throughout the surgery, we aim to limit the total dose of epinephrine, thereby limiting cost and minimizing the risk of epinephrine-related cardiovascular adverse events. Due to supply shortages, if 0.5% bupivacaine is unavailable then 0.25% bupivacaine will be substituted. All other dosing instructions will remain unchanged.

##### c. Rationale for Study Population

Our study population will be adult (18 years of age or older) patients undergoing arthroscopic shoulder surgery requiring visualization within the subacromial space. This includes primarily arthroscopic rotator cuff debridement or repair, arthroscopic subacromial decompression, arthroscopic subacromial bursectomy or bursal debridement, and arthroscopic distal clavicle resection, among other arthroscopic procedures. Only procedures performed in the seated, upright (ie, beach chair) position will be included as these cases present a unique challenge. The concept of “controlled hypotension” has been described as one technique for better visual clarity in the subacromial space, though this technique has been shown to affect cerebral blood flow and oxygenation [10]. Effective local hemostasis within the subacromial space to preserve visual clarity may obviate the need for controlled hypotension, thereby making surgery safer.

#### **d. Rationale for Study Design**

We propose a double-blinded randomized controlled trial to minimize bias and ensure similar baseline characteristics of the patients in each study group. Patients will be randomized to receive a pre-operative subacromial injection containing either bupivacaine with epinephrine, or bupivacaine alone. We will collect baseline characteristics of patients as well as potential confounding factors throughout and after the surgery to ensure that any difference in surgeon-rated visual clarity is a direct consequence of the intervention.

### **2. HYPOTHESIS AND OBJECTIVES**

#### **2.1. Purpose/Hypothesis**

**Purpose:** The aim of this study is to investigate the effect of a pre-operative subacromial injection containing epinephrine on the visual clarity during subacromial arthroscopic shoulder surgery.

**Hypothesis:** Pre-operative injection of epinephrine into the subacromial space will result in improved surgeon-rated visual clarity as well as decrease the need for increased arthroscopic irrigation pump pressure throughout the arthroscopic shoulder surgery as compared to injection not containing epinephrine.

#### **2.2. Primary Objectives**

To evaluate surgeon-rated visual clarity and the need for increased irrigation pump pressure during arthroscopic shoulder surgery.

#### **2.3. Secondary Objectives**

To evaluate mean arterial pressure, operative time, and any adverse events that occur during arthroscopic shoulder surgery.

#### **2.4. Potential Risks and Benefits:**

##### **a. End Points - Efficacy**

The use of epinephrine injection into the subacromial space prior to surgery may improve surgeon-rated visual clarity throughout surgery and obviate the need for increased irrigation pump pressure increases. Limiting the total dose of epinephrine required for adequate visualization helps to limit both the total cost and the potential for cardiovascular adverse events related to the use of epinephrine. Improved visual clarity may also decrease total operative time, which would further decrease the cost of the surgery. Obviating the need for increasing the irrigation pump pressure decreases the extravasation of fluid from the subacromial space into the soft tissues, thereby decreasing intra-operative and post-operative swelling leading to improved pain post-operatively.

##### **b. End Points - Safety**

While there are several published case reports describing epinephrine-related cardiovascular adverse events during shoulder arthroscopic surgery, all of these have occurred with the use of epinephrine within the irrigation fluid throughout the case. By limiting the use of epinephrine to the pre-operative subacromial injection and only the first 6 liters of arthroscopic irrigation fluid rather than throughout the entirety of the surgery, we hope to decrease the risk of these uncommon adverse events.

### **3. STUDY POPULATION**

#### **3.1. List the number of subjects to be enrolled.**

Thirty (n=30) subjects recruited from Texas will be sought for each group for a total enrollment of sixty (n=60). This is from a power analysis performed. The minimal clinically significant difference in visual acuity score (0-10) is 2 points, or 20%, as established in a prior study [1]. In order to ensure 80% power at an alpha of 0.05, a minimum of 26 patients are needed in each study group.

[1] D. Avery, et al., Arthroscopy 31(1) (2015) 12-8.

#### **3.2. Criteria for Recruitment**

Our study population will be adult (18 years of age or older) patients undergoing arthroscopic shoulder surgery requiring visualization within the subacromial space. This includes primarily arthroscopic rotator cuff debridement or repair, arthroscopic subacromial decompression, arthroscopic subacromial bursectomy or bursal debridement, and arthroscopic distal clavicle resection, among other arthroscopic procedures. Only procedures performed in the seated, upright (ie, beach chair) position will be included. Study participation will be contingent upon signed informed consent obtained prior to performing data collection or study procedures.

### **3.3. Inclusion Criteria**

Patients will be included who:

- Are individuals 18 years of age or older
- Are able to provide informed consent
- Undergo arthroscopic shoulder surgery in the seated upright (beach-chair) position requiring visualization within the subacromial space

### **3.4. Exclusion Criteria**

Subjects meeting any of the exclusion criteria at baseline will be excluded from participation. These criteria include those who:

- Are unable to provide informed consent
- Non-English speaker
- Have a history of adverse medication reaction to epinephrine
- Arthroscopic shoulder surgery not requiring visualization in the subacromial space or performed in the lateral position

### **3.5. Withdrawal Criteria**

Subject study participation will be discontinued upon patient request.

### **3.6. Subject Replacement**

There is no intervention or required follow-up after the pre-operative subacromial injection, so patient drop-out will be minimal.

## **4. TRIAL SCHEDULE**

Based on historic clinic data for the principal investigator and co-investigators, we anticipate meeting our enrollment target around 12 weeks from opening enrollment. Once enrolled, subjects will be randomized into either the epinephrine or placebo group. Surgeon-rated visual clarity score will be obtained immediately post-operatively.

## **5. STUDY DESIGN**

### **5.1. Summary of Study Design**

The study utilizes parallel groups with randomized assignments. Randomization will be performed prior to surgery and group designation will be placed within an opaque envelope in the patient's chart. The circulating nurse will prepare the pre-operative injection: study patients will receive an injection containing a total volume of 20 mL of bupivacaine with epinephrine (0.3 mL epinephrine in 30 mL of 0.5% bupivacaine) whereas control patients will receive an injection containing 20mL of 0.5% bupivacaine alone. The syringe will not be labeled, and the contents of the injection will not be disclosed to the surgeon to preserve blinding. The injection will be performed with an 18-gauge needle into the subacromial space via a posterior or lateral approach after positioning the patient in the beach chair position, but prior to prepping and draping. The first 10 liters of arthroscopic irrigation used during the case will contain a total of 10 mg of epinephrine (dilution 1:1000), then saline without epinephrine will be used for the remainder of the surgical procedure. Throughout the case, the mean arterial pressure of the patient will be monitored. At the conclusion of the surgical procedure, the surgeon will rate visual clarity on a visual analog scale from 0 to 10. We will also record changes in pump pressure from the initial pressure of 35mmHg during the surgical procedure. Finally, we will note any adverse events during or after the surgical procedure. In the unlikely event of an intra-operative or early post-operative adverse event that may be related to epinephrine administration, the presence or lack of epinephrine will be revealed to the anesthesiology team to ensure optimal treatment of the adverse event.

## **6. METHODS AND ASSESSMENTS**

### **6.1. Randomization and Blinding**

Simple randomization of enrolled subjects will occur prior to surgical intervention. A certified random number generator will be accessed that will generate a number to assign to the enrolled patient. A research coordinator will bring the randomization envelopes on the day of surgery. Blinding of enrolled subjects will be performed to prevent bias from occurring based on patient expectations of the procedure. To reduce recall bias, group allocation will be kept concealed from the investigator until the completion of visual clarity scoring at the conclusion of each surgical procedure.

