#### UTHealth CTRC DSMP Checklist

- Primary and secondary outcome measures
  - o Primary: surgeon-rated visual clarity score (visual analog scale 0 to 10), changes in intra-operative arthroscopic pump pressure
  - o Secondary: mean arterial pressure intra-operatively, total operative time, adverse events intra-operatively or post-operatively
  - o Inclusion: patients 18 years of age or older who are able to provide informed consent and who are to undergo arthroscopic shoulder surgery in the seated upright (beach-chair) position requiring visualization of within the subacromial space.
  - o Exclusion: Are unable to provide informed consent, non-English speaker, have a history of adverse medication reaction to epinephrine, and who are having arthroscopic shoulder surgery that does not require visualization within the subacromial space or performed in the lateral position.
  - o Sample size: Thirty (n=30) subjects recruited from Texas will be sought for each group for a total enrollment of sixty (n=60). This is from a power analysis performed. The minimal clinically significant difference in visual acuity score (0-10) is 2 points, or 20%, as established in a prior study. In order to ensure 80% power at an alpha of 0.05, a minimum of 26 patients are needed in each study group.
- List of participating enrolling clinics or data collection centers
  - o Memorial Hermann Memorial City Medical Center
  - o Memorial Hermann Surgery Center West Houston
  - o Memorial Hermann Orthopedic & Spine Hospital
  - o Memorial Hermann Surgery Center
  - o UT Physicians Orthopedics – Texas Medical Center
  - o UT Physicians Orthopedics – Memorial City
- Projected timeline
  - o Based on historic clinic data for the principal investigator and co-investigators, we anticipate meeting our enrollment target around 12 weeks from opening enrollment. Once enrolled, subjects will be randomized into either the epinephrine or placebo group. Surgeon-rated visual clarity score will be obtained immediately post-operatively.
- Target population distribution (e.g., women, minorities, etc.)
  - o The target population distribution will be the typical patients that the principal investigator and co-investigators schedules and operates on here at the UT Health and Memorial Hermann Health systems. Randomization will ensure that both groups will have similar demographic backgrounds.
- Data acquisition and transmission

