  - o Clinical assessments and images will be uploaded and stored on Epic and Centricity as is standard. The recorded assessments and images will be stored for study use for at least six years, with all study related data stored in Redcap.
  - o Demographic data (name, age, gender, weight, race) will be collected from medical records and stored in Redcap.
  - o Surgical data (start and stop times for procedure, type of procedure performed, mean arterial pressure) will be recorded and stored in Redcap.

- Objective clinical data (adverse events) will be collected during the post-operative period with information collected stored in Redcap.
  - Subjective clinical data (surgeon-rated visual clarity score, surgeon-requested increase in arthroscopic irrigation pump pressure) will be recorded and stored in Redcap.
  - Imaging data (none)
- Data entry methods
  - A linking log and data collection form will be used to protect subjects' PHI. All data will be entered and stored in a Redcap project drive to ensure maximal security and anonymity.
- Data analysis plan
  - Demographic variables and diagnostic outcomes will be compared using t-test for continuous variables and chi-square or Fisher exact test for categorical variables. A Mann-Whitney rank sum test will be used to compare median visual clarity scores.
- Quality assurance plan
  - To maintain accuracy, consistency and completeness of data, periodic audits and self-assessments will be conducted. The data will be cross-checked by the study coordinator and the PIs to maintain quality control.
- Reporting mechanisms of AEs/SAEs to the IRB, FDA, and NIDA
  - The principal investigator will report all AEs and SAEs occurring in clinical investigations to the IRB according to the UTHSC-Houston IRB policy. A definition of what constitutes an AE or SAE can be found below in this document as well as within the study protocol.
    - AEs will be compiled and submitted on an annual basis to the IRB. Each AE will require review from the investigator as soon as identified.
    - SAEs will be reviewed by the investigator as soon as identified, and all SAEs will be reported to the IRB within 48 hours of identification.
- Reporting mechanisms of IRB actions to NIDA
  - No drugs are involved in this study, so reporting to the NIDA will not be necessary.
- Report of changes or amendments to the protocol

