### 11.2. Statistical and Analytical Plans

Demographic variables and diagnostic outcomes will be compared using t-test for continuous variables and chi-square or Fisher exact test for categorical variables. A Mann-Whitney rank sum test will be used to compare median visual clarity scores. In the case where a serious medication-related adverse events occurs, we will also start an early analysis to determine the potential causes.

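### Both primary outcomes depend on the operating surgeon, but surgeon is not a named data item, a randomisation stratum or an analysis term; using it would be a low-cost gain in precision

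*Combined protocol and SAP*

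**What the plan says.** All references are to the combined protocol and SAP.

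- **Outcomes.** The DSMP checklist in section 9.3 gives: "Primary: surgeon-rated visual clarity score (visual analog scale 0 to 10), changes in intra-operative arthroscopic pump pressure". Section 5.1 says that at the end of the case "the surgeon will rate visual clarity on a visual analog scale from 0 to 10". The checklist's subjective data include the "surgeon-requested increase in arthroscopic irrigation pump pressure".
- **Who operates.** The checklist describes the target population as the "typical patients that the principal investigator and co-investigators schedules and operates on", so there is more than one surgeon. Their number and caseloads are not given.
- **Allocation.** Section 6.1: "Simple randomization of enrolled subjects will occur prior to surgical intervention". No stratum or block is mentioned.
- **Data items.** The checklist says: "Surgical data (start and stop times for procedure, type of procedure performed, mean arterial pressure) will be recorded and stored in Redcap". The demographic items describe the patient only. Section 1.2 d promises to collect "potential confounding factors throughout and after the surgery" but does not itemise them.
- **Analysis.** Section 11.2: "A Mann-Whitney rank sum test will be used to compare median visual clarity scores". Its other tests (t-test, chi-square, Fisher) are for demographic variables and diagnostic outcomes. None has a surgeon term.

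**The concern.** Surgeons may use a 0–10 scale differently, and may ask for more pressure at different thresholds. If so, that spread sits in the error term of both primary comparisons. Simple allocation can also give one arm more of a generous rater's cases by chance, which moves the observed difference in that trial. Neither effect makes the planned test invalid. At stake are precision and a prespecified way to deal with an uneven mix of raters.

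**Working it through.** **1. The plan's own figure.** Sections 3.1 and 11.1 give a 2-point difference, 80% power, alpha 0.05 and 26 per group, but no SD and no statement of one- or two-sided testing. Taking a two-sided test, the normal approximation gives SD = 2 × √(26/2) / (1.960 + 0.842) = 7.211 / 2.802 = 2.57. With the t-test, 26 per group corresponds to an SD of about 2.47–2.52. I use a total SD of 2.5. At 30 per arm the t-test then has 86.1% power.

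**2. Chance imbalance under simple allocation (equal caseloads assumed).** With three surgeons of 20 cases, one surgeon's cases split 2:1 or worse with probability 0.115, so for at least one of the three it is 1 − (1 − 0.115)³, about 31%. With five surgeons of 12 it is 1 − (1 − 0.388)⁵ = 91%. If 10–30% of score variance lies between surgeons, rater mix adds a random arm difference with SD of about 0.17–0.33 points.

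**3. Variance share (assumed differences).**
- One of four equal-volume surgeons rating 2 points higher: 2² × ¼ × ¾ = 0.75, and 0.75 / 6.25 = 12%. Removing it is worth 60 / 0.88 = 68 patients instead of 60.
- Four surgeons at 0/1/2/3: variance 1.25, and 1.25 / 6.25 = 20%, worth 60 / 0.80 = 75 patients.

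**4. Simulated power for clarity.** N = 60, 2-point difference, normal scores, total SD 2.5, 20,000 trials per cell, simulation error about ±0.5 point. Planned: simple allocation with Mann-Whitney. Proposed: surgeon-stratified blocks with a linear model of pooled ranks on arm and surgeon.

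| Caseloads (assumed) | Surgeon differences (assumed) | Planned | Proposed | Gain, points |
|---|---|---|---|---|
| 2×30 | none | 83.8% | 84.4% | 0.6 |
| 4×15 | none | 84.2% | 84.0% | −0.2 |
| 6×10 | none | 83.8% | 84.2% | 0.4 |
| 40/10/6/4 | none | 83.8% | 84.1% | 0.3 |
| 30/10/8/6/4/2 | none | 83.3% | 84.0% | 0.7 |
| 4×15 | one +1 | 83.8% | 85.2% | 1.4 |
| 40/10/6/4 | smallest-volume +2 | 83.8% | 85.2% | 1.4 |
| 6×10 | one +2 | 83.6% | 87.1% | 3.5 |
| 4×15 | one +2 | 83.6% | 87.6% | 4.0 |
| 40/10/6/4 | largest-volume +2 | 83.5% | 89.1% | 5.6 |
| 2×30 | one +2 | 84.0% | 89.7% | 5.7 |
| 30/10/8/6/4/2 | largest-volume +2 | 83.5% | 89.3% | 5.8 |
| 4×15 | 0/1/2/3 | 83.3% | 91.2% | 7.9 |

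Type I error was .047–.053 for the planned method and .048–.053 for the proposed one. Integer 0–10 scores with a ceiling gave the same picture (4×15, 10,000 trials): none 81.8% v 82.5%, one +2 81.6% v 86.3%, 0/1/2/3 81.7% v 88.8%.

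**5. Allocation and analysis should match.** Adjusting after simple allocation costs power when surgeons do not differ: from 0.4 points (2×30, 83.8% to 83.4%) to 3.2 points (6×10, 83.8% to 80.6%). In the other direction, an unadjusted Mann-Whitney test after stratified blocks becomes conservative when surgeons differ (type I error as low as .027). A van Elteren test after stratified blocks costs up to 2.4 points when surgeons do not differ (6×10, 83.8% to 81.4%), which is why the rank model is preferred.

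**The case against.** Much of the case against stands and limits the point.

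- **No stated goal is missed.** At the back-solved SD, planned power for clarity is above 80% in every scenario. This is an efficiency choice, and it stays graded as one to consider.
- **The gain rests on assumptions.** The largest figure needs four surgeons covering a 3-point range, wider than the 2-point effect sought. With one of four at +1 the gain is 1.4 points.
- **The data list is not exhaustive.** It is a monitoring checklist, not a case report form; it omits the medications that section 8.6 says will be documented. Section 1.2 d could cover surgeon, and the medical record would probably identify the surgeon. What is missing is a named field and a prespecified use of it.
- **Blocks bring predictability that simple allocation does not have.** With strata of 15, block sizes 2 and 4, and a reveal after each case, a surgeon who knew the sizes could be certain of about 10% of assignments and guess about 71% correctly, against 50% now. Concealment has to come with the blocks. The circulating nurse, who prepares the injections, will still see allocations as they arise.
- **Adjustment alone sometimes gives most of the gain.** In separate runs (6,000 each; planned / simple and adjusted / blocks and adjusted), 4×15 at 0/1/2/3 gave 83.9 / 89.7 / 91.0%. For 6×10 with one +2, however, blocks gave nearly all of it: 83.2 / 83.3 / 87.3%.

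A reader might infer that the planned comparison is biased by surgeon, or that the trial cannot attribute a clarity difference to the injection without adjusting. Neither follows: randomisation keeps the unadjusted comparison unbiased, and adjustment only sharpens it. A reader might also infer a power loss for pump pressure under the plan. Section 11.2 does not clearly assign that outcome a test, so there is no planned analysis against which to measure a loss.

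**Conclusion.** The point holds as an inexpensive improvement, not as an error. The person who determines both primary outcomes appears nowhere in the listed data, the allocation or the tests. For clarity, using surgeon in both allocation and analysis loses no power beyond simulation error when surgeons do not differ. It gains about 1 point when they differ little, about 4–6 points when one of several rates 2 points higher (only about 1 if that surgeon has few cases), and about 7–8 points when four are spread at 0/1/2/3. These figures assume a two-sided test, a total SD of 2.5 and invented surgeon numbers, caseloads and differences, so they are a scenario range and not an estimate for this trial.

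**What to change.** 1. **DSMP checklist, surgical data:** add a coded operating-surgeon field.
2. **Section 6.1:** replace simple randomisation with computer-generated permuted blocks of undisclosed, randomly varying size, stratified by operating surgeon, with one envelope set per surgeon. The coordinator already brings the envelopes, and section 6.3 a places screening after the decision to operate. Withhold allocation from surgeons until all clarity scoring is complete, and bring sections 6.1 and 8.5, which allow disclosure after each case, into line. Keep a sealed allocation record available so that the safety unmasking in section 5.1 still works.
3. **Section 11.2:** make the primary clarity test a linear model of the pooled ranks (mid-ranks for ties) on arm and surgeon, two-sided at 0.05. Report a surgeon-adjusted difference in points with a 95% CI. Name the same model for pump-pressure change.

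**Cost:** one data field, slightly more complex allocation, a later reveal to surgeons and patients (enrolment is expected to take about 12 weeks, section 4), and an amendment with IRB approval, which the checklist requires. No extra patients are needed.

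**Fallback, if enrolment has begun or allocation must be revealed after each case:** keep simple randomisation and Mann-Whitney as primary, record surgeon, and prespecify the surgeon-adjusted rank model as a sensitivity analysis only, because adjusting after simple allocation costs up to about 3 points if surgeons do not differ.

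### Simple randomization of 60 patients does not guarantee the 30 sought or the stated minimum of 26 per group, nor the similarity the plan says it ensures; the cost in power is small.

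*Combined protocol and SAP*

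**What the plan says.** Section 6.1 gives the allocation method: "Simple randomization of enrolled subjects will occur prior to surgical intervention". A random number generator supplies the assignment, and a coordinator brings the envelopes. The plan mentions no blocking, stratification, minimization or per-arm limit.

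Sections 3.1 and 11.1 and the DSMP checklist in 9.3 seek 30 patients per group, 60 in total. On the number required, 3.1 says: "In order to ensure 80% power at an alpha of 0.05, a minimum of 26 patients are needed in each study group". The checklist repeats this, and 11.1 gives the same 26.

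On comparability, section 1.2.d proposes the design "to minimize bias and ensure similar baseline characteristics of the patients in each study group", and the checklist says: "Randomization will ensure that both groups will have similar demographic backgrounds".

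Eligibility in 3.2 is broad. It runs from bursal debridement to cuff repair "and arthroscopic distal clavicle resection, among other arthroscopic procedures". Procedure type is recorded (checklist, data acquisition), but section 11.2 names only unadjusted tests: t, chi-square or Fisher, and Mann-Whitney for visual clarity.

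**The concern.** The plan attributes three properties to its randomization that simple randomization does not have: fixed group sizes, a floor of 26 per group, and similar groups. If 6.1 is followed exactly, the stated minimum may be missed without any protocol deviation or dropout, and the report would have to explain why.

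Similarity matters too. Procedure type could plausibly affect bleeding, operating time and pump pressure, although the documents do not say so. In a trial of 60 the case mix may differ between arms by chance, and neither the allocation nor the specified analysis deals with that.

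**Working it through.** **Inputs.** Total 60, 30 sought per group, 26 needed for 80% power at alpha 0.05, difference 2 points (section 3.1). Simple randomization (6.1). The documents give no allocation probability, sidedness or SD. I assume 1:1 from the 30 + 30 target and a two-sided test, and back-solve the SD.

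**1. The plan's 26.** It cannot be reproduced directly without an SD. With the normal approximation, n per group = 2 × (1.960 + 0.842)² × SD² / 2² ≈ 3.925 × SD². This rounds up to 26 for an SD of 2.53 to 2.57 (3.925 × 2.53² ≈ 25.1; 3.925 × 2.57² ≈ 25.9). A t-test calculation gives 2.48 to 2.52. I use SD 2.5, a standardized difference of 2 / 2.5 = 0.8.

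**2. Group sizes.** Let X, the size of one arm, be Binomial(60, 0.5).

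- P(X = 30) = 0.103.
- P(one arm below 26) = 2 × P(X ≤ 25) = 2 × 0.1225 = 0.245.
- With fewer evaluable patients, the second figure rises to 0.358 at 58 and 0.504 at 56.

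**3. What unequal arms cost.** For arms a and b, the effective size per arm is 2ab / (a + b). At 25/35 it is 2 × 25 × 35 / 60 = 29.2. Power is for a two-sided t-test, as an approximation to the planned Mann-Whitney test.

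| Split | Effective n per arm | Power |
|---|---|---|
| 30/30 | 30.0 | 86.1% |
| 25/35 | 29.2 | 85.2% |
| 20/40 | 26.7 | 81.9% |
| 26/26 | 26.0 | 80.7% |

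Averaged over all splits that simple randomization can produce, power is 85.5%, a loss of 86.1 − 85.5 = 0.6 points. Effective size falls below 26 only at 19/41 or worse, with probability 0.006.

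**4. Case mix.** The procedure mix is not stated, so the repair share is an assumption. Taking each patient to be a cuff repair with probability 0.3, 0.5 or 0.7, the arms differ in repair share by 20 percentage points or more in about 10%, 13% and 10% of trials. If exactly 30 of the 60 were repairs, the figure would be 15.5%.

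**5. What blocks would do.** Blocks of 4 and 6 in random order leave a difference between arms of at most 3 in any one list. At 60 patients in one list the difference must be even, so it is at most 2 and the smaller arm is at least 29. With two strata the difference is at most 3 + 3 = 6, so the smaller arm is at least (60 − 6) / 2 = 27. In simulation, exactly 30/30 occurs in about 77% of trials with one list and 55% with two strata (half repairs assumed).

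Keeping simple randomization would instead need 67 patients to bring the chance of an arm below 26 to 5%.

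**6. Predictability.** If every past allocation were known, guessing the under-represented arm would be right about 69% of the time with these blocks, against 50% under simple randomization (simulation).

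**The case against.** The strongest reply is that simple randomization is a valid method and the consequences here are slight. A reader might infer from the 24.5% that the trial has a one-in-four chance of being underpowered. The documents do not support that. The 26 is the requirement for two equal groups, and with 60 patients in all a 25/35 split carries more information than 26/26. This part of the reply stands in full.

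It is also fair that the 30 is described as sought, so it reads as a target, and that the minimum of 26 is met in 100 − 24.5 = 75.5% of trials. The method does not guarantee these sizes, but that is not to say it cannot deliver them.

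A reader might further infer that case-mix imbalance would bias the result. It would not in expectation. Chance imbalance is already allowed for in the test's error rate, and the recorded procedure type would permit an adjusted analysis, though 11.2 specifies none. The size of the imbalance rests on an assumed procedure mix.

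Finally, blocking has a risk of its own. Section 6.1 conceals allocation from the investigator only until each case is scored, and 8.5 lets patients learn their arm straight afterwards. With a subjective, surgeon-rated outcome, predictable blocks could do more harm than unequal arms. The 69% is an upper-end figure, since knowledge would be partial across several surgeons and sites, but the fix must deal with it.

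What remains is the inconsistency: the plan states a minimum and a similarity that its allocation method does not secure.

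**Conclusion.** The point holds as a modest inconsistency that is cheap to repair. Under 1:1 simple randomization of 60 patients, 30/30 occurs in about 10% of trials and an arm falls below the stated minimum in 24.5%. These figures rest only on the 1:1 assumption and on all 60 patients being evaluable.

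The cost in power is about one point at 25/35, given the back-solved SD of 2.5. A between-arm gap of 20 points or more in cuff-repair share would arise in about 10 to 13% of trials if 30 to 70% of cases are repairs, which is an assumption. Neither result shows an underpowered trial or a biased comparison. The claims that similarity is ensured are too strong for this method.

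**What to change.** - **Section 6.1, allocation:** replace simple randomization with a computer-generated 1:1 list in permuted blocks of randomly varying, undisclosed size, for example 4 and 6. Optionally use two strata by planned cuff repair, yes or no. This can be known in time, because screening follows the decision to operate (6.3.a). One list secures the group sizes but not the case mix; the strata address the latter. Neither always gives exactly 30/30.
- **Sections 6.1 and 8.5, concealment:** make this change together with the first. Keep allocation concealed from surgeons and patients until the last patient's visual clarity score is recorded, leaving the adverse-event disclosure in 5.1 as it is.
- **Section 1.2.d and the checklist in 9.3:** change *ensure* and *will ensure* to *is intended to give*.

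The cost is a few sentences and a different list, with no extra patients or visits; the envelopes and coordinator are already in place. Patients would wait longer to learn their arm. Allocation becomes somewhat more predictable than under simple randomization, which the varying block sizes and longer concealment limit.
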